### 11.3 Planned Interim Analyses

#### 11.3.1 Safety Review

An interim safety review may include enrollment and demographic information, medical history, concomitant medications, physical examination, dosing compliance, and solicited adverse events. Additional data may be requested by the DSMB, and interim statistical reports may be generated as deemed necessary and appropriate by DMID. The DSMB may receive data in aggregate and presented by treatment arm. The DSMB may also be provided with expected and observed rates of the expected AEs in an unblinded fashion and may request the treatment assignment be unblinded for an individual subject if required for safety assessment. The DSMB will review grouped and unblinded data in the closed session only. The DSMB will meet and

review this data at scheduled time points or ad hoc as needed during this trial as defined in the DSMB charter. As an outcome of each review/meeting, the DSMB will make a recommendation as to the advisability of proceeding with the study treatments, and to continue, modify, or terminate this trial.

Additionally, this trial will be monitored to determine if any of the study halting rules described in Section 9.5.1 are met.

### **11.3.2 Interim Analysis of Efficacy, Futility, and Safety**

There will be no interim analysis of efficacy or futility. An interim analysis will be performed to assess the assumptions used for sample size calculations including rate of adequate clinical improvement, rate of evaluable subjects and the frequency of enrolled subjects with PCT  $\leq 0.25$  ng/mL

Assumptions underlying the original target sample size of 420 subjects were assessed by a planned, interim, blinded analysis after approximately 210 subjects completed or terminated from the study. Original assumptions were that the overall rate of clinical improvement at Visit 3 would be 80% and there would be no more than 15% unevaluable subjects (i.e. withdraw, fail to complete Visit 3 or didn't meet other inclusion criteria for the according-to-protocol population at Day 5, as defined in Section 11.4) In this interim analysis, the required sample size needed for 80% power to rule out a 12.5% increase in the clinical improvement rate with antibiotic therapy compared to placebo was computed using the observed overall rate of clinical improvement across both treatment groups and the observed proportion of subjects eligible for a per-protocol analysis at Day 5. Due to findings at the interim analysis, new sample size estimates have been generated to account for actual observed rates of clinical improvement and protocol deviations that preclude inclusion in the primary analysis.

## **11.4 Final Analysis Plan**

The intention-to-treat (ITT) analysis population will consist of all randomized subjects. According-to-protocol (ATP) analysis populations will consist of subjects with no major protocol deviations regarding inclusion/exclusion criteria that consumed 5 doses of study product by Visit 3. The first dose of study drug should be taken within 24 hours of randomization. Subjects who miss a scheduled dose but resume the recommended dosing schedule within 24 hours remain eligible for ATP. However, in order for a subject to be eligible for the ATP-5 analysis, Visit 3 should be performed on or after the last day of study drug consumption while remaining within the 5+3 window. The ATP-5 analysis population will have the further restriction that the subjects must have completed an in-person Visit 3 within the protocol-defined time window. The ATP-11 analysis population will consist of the ATP analysis population with the further restriction that the subjects must have completed Visit 4 within the protocol-defined time window. The ATP-28

analysis population will consist of the ATP analysis population with the further restriction that the subjects must have completed Visit 5 within the protocol-defined time window.

Unless otherwise stated, all hypothesis tests and confidence intervals will be two-sided with  $\alpha=0.05$ . Statistical tests and confidence intervals will not correct for multiplicity.

#### **11.4.1 Primary Analysis**

The non-inferiority of placebo versus azithromycin with respect to clinical improvement on at Visit 3 (as defined in Section 3.2.1), using a non-inferiority margin of 12.5%, will be determined for the ITT analysis population using a 95% confidence interval of the difference in proportions of clinical improvement as constructed using multiple imputation of clinical improvement with linear regression. The study Day that Visit 3 occurred on will be included as a covariate. A lower bound of the confidence interval greater than -12.5% will result in the conclusion of non-inferiority of placebo. At minimum, the imputation model will utilize available information collected at baseline and any completed study visits. Further details of the imputation model will be described in the SAP.

#### **11.4.2 Secondary Analyses**

1. The non-inferiority analysis of placebo versus azithromycin with respect to clinical improvement at Visit 3 (as defined in Section 3.2.1), using a non-inferiority margin of 12.5%, will be repeated as described in Section 11.4.1 using the ATP-5 analysis population.
2. The non-inferiority analysis of placebo versus azithromycin with respect to clinical improvement at Visit 4 (as defined in Section 3.2.1), using a non-inferiority margin of 12.5%, will be repeated as described in Section 11.4.1 using the ITT analyses population as well as ATP-11 analysis population.
3. The non-inferiority analysis of placebo versus azithromycin with respect to clinical improvement at Visit 5 (as defined in Section 3.2.1), using a non-inferiority margin of 12.5%, will be repeated as described in Section 11.4.1 using the ITT analyses population as well as ATP-28 analysis population.
4. Using the ATP-11 and ATP-28 analysis populations, respectively, the mean number of days of antibiotic use from Day 1 until Visit 4 or Visit 5 will be computed for placebo versus azithromycin, in addition to an estimated difference in means and associated 95% confidence intervals. The significance of the difference in means will be tested by a t-test.
5. Using the ATP-11 and ATP-28 analysis populations, respectively, the proportion of subjects with one or more return visits to a physician's office or urgent care for persistent or worsening LRTI at any time after randomization by Visit 4 or by Visit 5 will be

computed for placebo versus azithromycin, in addition to an estimated odds ratio and associated 95% confidence intervals. The significance of the difference in proportions will be tested by a Fisher's Exact Test.

6. Using the ATP-11 and ATP-28 analysis populations, respectively, the proportion of subjects with one or more emergency department visits for persistent or worsening LRTI at any time after randomization by Visit 4 or by Visit 5 will be computed for placebo versus azithromycin, in addition to an estimated odds ratio and associated 95% confidence intervals. The significance of the difference in proportions will be tested by a Fisher's Exact Test.
7. Using the subsets of the ATP-11 and ATP-28 analysis populations, respectively, consisting of subjects not hospitalized at the enrollment and randomization visit, the proportion of subjects with one or more hospitalizations for persistent or worsening LRTI at any time after randomization by Visit 4 or by Visit 5 will be computed for placebo versus azithromycin, in addition to an estimated odds ratio and associated 95% confidence intervals. The significance of the difference in risk will be tested by a Fisher's Exact Test.
8. Using the ATP-11 and ATP-28 analysis populations, respectively, the proportions of subjects exhibiting improvement in at least one presenting symptom (Table 1) by Visit 4 or by Visit 5 will be computed for placebo versus azithromycin, in addition to an estimated odds ratio and associated 95% confidence intervals. The significance of the difference in proportions will be tested by a Fisher's Exact Test. The analysis will be repeated, analyzing each symptom individually.
9. The Day 5 DOORs (an ordinal outcome defined in Section 3.2.3) will be compared between the placebo and azithromycin arms. The sum of the probability that a randomly selected subject will have a better DOOR if assigned to the placebo arm plus one-half the probability of equal DOORs will be estimated. The null hypothesis to be tested is that the probability is equal to 0.50 (lack of superiority of azithromycin therapy). The analysis will be carried out using the ITT analysis population, with missing DOOR values (treated as continuous) imputed using multiple imputation, utilizing linear regression models. The analysis will be repeated using the ATP-5 population. At minimum, the imputation model will utilize available information collected at baseline and any completed study visits. Further details of the imputation model will be described in the SAP. The Mann-Whitney U statistic will be combined across the imputed datasets to give the test statistic and Rubin's Rules used to define distribution of the test statistic under the null hypothesis. A point estimate of the estimand will be computed by dividing combined test statistic by the number of pairwise comparisons and a 95% confidence interval of the estimand will be computed by inverting the described test of the null hypothesis.

10. Using the ATP-5 analysis population, forest plots of 95% confidence intervals for the difference in proportions of subjects with each solicited event (a component of DOOR) collected through Visit 3, for each severity threshold (mild or greater, moderate or greater, or severe) will be generated. Tests for differences in proportions between treatment arms will be given by Fisher's exact tests.
11. Using the ATP-5 analysis population, a forest plot of 95% confidence intervals for the difference in proportions of subjects with one or more visits to an ED, one or more visits to an outpatient clinic, or one or more visits to an urgent care center or one or more hospitalizations for persistent or worsening LRTI at any time after randomization (a component of clinical improvement and DOOR) will be generated. Tests for differences in proportions between treatment arms will be given by Fisher's exact tests.
12. Using the ATP-5 analysis population, for each qualifying vital sign (temperature, pulse, respiratory rate, or pulse oximetry) and symptom (cough, sputum production, chest pain, or difficulty breathing), improvement in the sign or symptom at Visit 3 compared to baseline in subjects with the symptom or vital sign abnormality at baseline (a component of clinical improvement and DOOR) will be analyzed. A forest plot of 95% confidence intervals for the difference in proportions of subjects with improvement in the symptom or sign will be generated. Tests for differences in proportions between treatment arms will be given by Fisher's exact tests.
13. Using the ATP-5 analysis population, for each qualifying symptom (cough, sputum production, chest pain, or difficulty breathing), deterioration in the symptom at Visit 3 compared to baseline (a component of clinical improvement and DOOR) will be analyzed in subjects having the symptom at baseline. A forest plot of 95% confidence intervals for the difference in proportions of subjects with deterioration in the symptom will be generated. Tests for differences in proportions between treatment arms will be given by Fisher's exact tests.
14. Using the ATP-5 analysis population, for each vital sign (temperature, pulse, respiratory rate, or pulse oximetry), new occurrence of a vital sign abnormality at Visit 3 compared to baseline (a component of clinical improvement and DOOR) will be analyzed in subjects without the sign abnormality at baseline. Additionally, the proportion of subjects with fever in the 24 hours preceding or at Visit 3 (fever is defined as  $\geq 37.8$  °C or 100.0 °F, measured anywhere on the body), unless related to a new process that is unrelated to the prior diagnosis of LRTI will be analyzed. A forest plot of 95% confidence intervals for the difference in proportions of subjects with new occurrence of a sign abnormality at Visit 3 compared to baseline or fever in the 24 hours preceding or at Visit 3 will be generated. Tests for differences in proportions between treatment arms will be given by Fisher's exact tests.

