**Secondary:**

1. To compare groups receiving azithromycin versus placebo with regard to all antibiotic use by Days 11 and 28.
2. To compare groups receiving azithromycin versus placebo with regard to return visits to a physician's office or urgent care by Days 11 and 28.
3. To compare groups receiving azithromycin versus placebo with regard to emergency department visits by Days 11 and 28.
4. To compare groups receiving azithromycin versus placebo with regard to hospitalization by Days 11 and 28 if not hospitalized at the enrollment and randomization visit.
5. To compare groups receiving azithromycin versus placebo with regard to improvement in presenting symptoms by Days 11 and 28.
6. To compare the efficacy of azithromycin versus placebo on Day 11 in subjects with suspect LRTI and PCT levels of  $\leq 0.25$  ng/mL at enrollment using a non-inferiority approach.
7. To compare the efficacy of azithromycin versus placebo on Day 28 in subjects with suspect LRTI and PCT levels of  $\leq 0.25$  ng/mL at enrollment using a non-inferiority approach.
8. To compare the efficacy of azithromycin versus placebo in subjects with suspected LRTI and PCT levels of  $\leq 0.25$  ng/mL at Day 5 using a superiority approach, employing the "Response Adjusted for Days of Antibiotic Risk (RADAR)" methodology.
9. To compare groups receiving azithromycin versus placebo in regard to solicited events by Day 5.
10. To compare groups receiving azithromycin versus placebo in regard to hospitalization or visits to an ED, outpatient clinic, or urgent care center for worsening or persistent LRTI after randomization by Day 5.

11. To compare groups receiving azithromycin versus placebo in regard to improvement in vital sign abnormalities or symptoms present at enrollment, on Day 5.
12. To compare groups receiving azithromycin versus placebo in regard to new vital sign abnormalities or symptoms on Day 5, or deterioration in symptoms relative to the enrollment visit on Day 5.

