## **6.2 Dosage, Preparation and Administration of Study Intervention/Investigational Product**

### **6.2.1 Azithromycin and Placebo**

Azithromycin 500 mg or placebo (administered orally as two 250 mg capsules or two matching placebo capsules) as a single dose within 24 hours of randomization, followed by Azithromycin 250 mg or placebo (administered orally as one 250 mg capsule or one matching placebo capsule) once daily for 4 days (Day 2 through Day 5).

Capsules should be maintained as dispensed and not scored, cut, crushed, or otherwise divided for ease of swallowing. The capsules will be administered with water sufficient for the subject to swallow the required number of capsules.

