6.3.2. According-to-Protocol (ATP) Cohorts

Subjects in an ATP analysis require no major protocol deviations and consumed 5 doses of study product by D5V. Subjects who miss a scheduled dose but resume the recommended dosing schedule within 24 hours remain eligible for ATP. As an exception, subjects who missed this window by at most 3 hours will be included in this population. What constitutes a major protocol deviation was assessed on a case-by-case basis by a DMID/VTEU/ARLG committee prior to any member of the committee being unblinded to treatment assignments. No major protocol deviations contributing to exclusion from ATP were identified. Subjects in an ATP analysis will be analyzed as treated. The ATP-5 (or ATP-11/ATP-28) populations will restrict subjects to those that meet the ATP requirements and furthermore completed their D5V (or D11V or D28V) in person

within the protocol defined time window and had sufficient data to define clinical improvement at D5V (or D11V or D28V). Missingness of DOOR will not exclude subjects from these ATP populations.

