6.5.5. Number of Days of Antibiotic Use at D5V, D11V, or D28V

Analysis involving comparisons of the number of days of antibiotic use will consider all antibiotic use from Day 1 onwards including study antibiotics and non-study antibiotics for systemic use. The number of days of antibiotic use is defined as the actual number of days of antibiotic use (any amount of study product that is not placebo, or any amount of other systemic antibiotic) from Day 1 to D5V study day inclusive for D5V, from Day 1 to D11V study day inclusive for D11V, and from Day 1 through D28V study day inclusive for D28V. For subjects that received placebo as study product, it is counted as the number of days of systemic antibiotic as determined solely from the concomitant medication form. For subjects that receive actual antibiotic as study product, it is counted as the number of days that the subject received any amount of either study product or a non-study systemic antibiotic, as determined from the concomitant medication form. Note that missed doses of study product do not necessarily lower the number of days of antibiotic use as long as a separate dose of antibiotic (study product antibiotic or concomitant medication antibiotic) was received on that day. The number of days of antibiotic use is missing (at D5V, D11V, and D28V) if the product administration record was not completed for the subject and the subject did not have non-study systemic antibiotic use during the study period recorded as a concomitant medication.

The number of days of antibiotic use at the time of analysis will be determined from the product administration records and concomitant medication records only. Data management activities and site queries (outside the scope of this document) prior to data lock will ensure concomitant medication records are as complete as possible and consistent with other records (i.e., AEs and medically attended visit records in the clinical database). The number of days of antibiotic use for a concomitant medication will be calculated as the medication end date minus the medication start date plus one day. Days will not be double counted if multiple systemic antibiotics (including antibiotic as study product) are taken on the same day. Systemic antibiotic use will not be counted for days that fall outside of the range being considered for each subject (Days 1 to D5V study day, or Day 1 to D11V study day, or Day 1 to D28V study day).

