8.2.4. Sensitivity Analysis of Clinical Improvement, ITT Analysis Population

Robustness of the multiple imputation model for ITT analysis population will be assessed by using tipping point analysis using linear regression as described in Section 8.2.1 using linear regression adjusting for treatment group and centered study day of D5V (or D11V, D28V). A point estimate of the difference in rates of clinical improvement, placebo relative to azithromycin and its 95% CI from the linear regression model will be reported. The results of this sensitivity analyses will be provided in [Table 27](#) for D5V, [Table 28](#) for D11V and [Table 29](#) for D28V.

8.2.5. Analysis of Number of Days of Antibiotics Use at D11V and D28V Using ATP Analysis Populations

Using the ATP-11 and ATP-28 analysis populations, respectively, the mean number of days of antibiotic use from Day 1 until D11V or D28V will be computed based on the definitions from Section 6.5.5 for the placebo group and the azithromycin group, in addition to an estimated difference in means for the placebo group relative to the azithromycin group using the t-test and its associated 95% CIs calculated based on t-test. The significance of the difference in means will be tested by a t-test and results from the Satterthwaite method will be provided in [Table 30](#) and [Table 31](#). An individual listing of days of antibiotics use is provided in [Listing 16](#).

8.2.6. Analysis of Medically Attended Events at D11V and D28V Using ATP Analysis Populations

Proportions of subjects with one or more return visits to a physician's office or urgent care, one or more emergency department visits, or one or more hospitalizations for persistent or worsening LRTI at any time after randomization by D11V or D28V will be produced for D11V and D28V and results will be reported in [Table 32](#), [Table 33](#), and [Table 34](#). Tests for differences in proportions, placebo relative to azithromycin, will be given by Fisher's Exact Test. In addition, an estimated odds ratio and its associated 95% CI calculated using the Wald Method will be provided. [Listing 19](#) contains all medically attended visits while [Listing 20](#) provides a listing of all hospitalizations.

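### The only test for the antibiotic-use objective is essentially fixed by the assigned azithromycin course, and non-study antibiotic use is not analysed as its own endpoint

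*Protocol*

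**What the plan says.** Secondary objective 1 is "To compare groups receiving azithromycin versus placebo with regard to all antibiotic use by Days 11 and 28" (Protocol 3.1). Protocol 11.4.2 item 4 turns this into one comparison: "the mean number of days of antibiotic use from Day 1 until Visit 4 or Visit 5 will be computed for placebo versus azithromycin", in ATP-11 and ATP-28 respectively. SAP 8.2.5 adds the test, using the Satterthwaite form: "The significance of the difference in means will be tested by a t-test". Results go to Tables 30 and 31.

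SAP 6.5.5 defines the count. It "will consider all antibiotic use from Day 1 onwards including study antibiotics and non-study antibiotics for systemic use". For placebo subjects it is "counted as the number of days of systemic antibiotic as determined solely from the concomitant medication form". A day on which several antibiotics are taken counts once, and days after the visit are not counted.

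ATP-11 and ATP-28 are subsets of the ATP population. Its members must have "consumed 5 doses of study product by Visit 3" (Protocol 11.4) or, in SAP 6.3.2, "consumed 5 doses of study product by D5V". Dosing is once a day on Days 1 to 5 (Protocol 6.2.1), so five doses means about five antibiotic days in the azithromycin arm.

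**The concern.** In these populations the azithromycin mean is about five days plus any rescue days. The placebo mean is rescue days alone. A test of equal means asks whether placebo subjects accumulate about five more rescue days each than azithromycin subjects, which nobody doubts in advance.

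The design sections describe the trial as a strategy to reduce antibiotic prescribing. A natural question is how far withholding azithromycin moves prescribing to a later rescue course, and the planned p-value cannot inform it.

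The choice of population adds to the problem. Protocol 9.5.2 allows study product to be stopped when off-study antimicrobials are needed. A subject who stops before five doses leaves the ATP population, and Protocol 11.2 itself names rescue medication as a source of per-protocol loss. Some of the rescue use of interest can therefore be removed, after randomisation, from the only test of this objective.

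**Working it through.** The documents give no sample size, effect size or SD for this test, so there is no stated figure to reproduce.

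**Inputs from the documents.** Five dosing days in the azithromycin arm. ATP-5 target of 560, or 280 per arm (674 × (1 - 0.169) = 560). No size is given for ATP-11 or ATP-28, so 280 is a proxy.

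**Assumptions.** Rescue proportions rA (azithromycin) and rP (placebo), and course length L. The documents give none of these, so ranges are used.

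**Formulas** (placebo minus azithromycin, no overlap with study drug):

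- Difference = L·rP - (5 + L·rA)
- SE = L·√[(rP(1 - rP) + rA(1 - rA))/n]

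**Equal rescue.** The difference is -5 whatever the rate. At n = 280, rA = rP = 5% and L = 7, SE = 7 × √[(0.0475 + 0.0475)/280] = 0.129, so t is about 39 in size. From 2% rescue with 7-day courses to 30% with 10-day courses, t falls from about 60 to about 13. Even with 20 per arm, power across that range is 93% or more.

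**Unequal rescue** (n = 280, L = 7):

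| Rescue, azithromycin vs placebo | Planned difference, total days (95% CI) | z | Difference in non-study days |
|---|---|---|---|
| 5% vs 5% | -5.00 (-5.25 to -4.75) | -38.8 | 0.00 |
| 5% vs 10% | -4.65 (-4.95 to -4.35) | -30.0 | +0.35 |
| 5% vs 15% | -4.30 (-4.64 to -3.96) | -24.6 | +0.70 |
| 5% vs 25% | -3.60 (-4.00 to -3.20) | -17.8 | +1.40 |
| 5% vs 40% | -2.55 (-2.99 to -2.11) | -11.4 | +2.45 |

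In the 5% vs 15% row, a direct comparison of the proportions with rescue would have about 98% power.

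**When is the null true?** Setting the difference to zero gives rP - rA = 5/L. That is 71 percentage points for 7-day courses and 50 points for 10-day courses.

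**Effect of the counting rules.** The formulas ignore the rules on overlap and on the visit cut-off.

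- Overlap: suppose every 7-day rescue course on azithromycin overlaps all five study days, so each adds only two. At 5% vs 5% the difference is 0.35 - (5 + 0.10) = -4.75. The null then needs rP = (5 + 2 × 0.05)/7 = 73%, still a gap of 68 points.
- Cut-off: truncating courses at the visit shortens L and widens the gap needed.

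Neither rule changes the conclusion.

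**The case against.** The strongest reply is that the analysis does what the objective says. The objective names all antibiotic use, and total days is a fair measure of net exposure, the benefit described in Protocol 2.3.2. This stands: the estimate and its interval should be kept. A reader might infer that counting study drug contradicts the objective, but the wording does not support that.

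A reader might also infer that rescue use is never compared between arms. That is wrong. Persistent or worsening LRTI is defined by receipt of a non-study antibiotic for LRTI (SAP 6.5.1.4 and 6.5.2.3). Such visits and hospitalisations are tested by Fisher's exact test in Tables 32-34 (D11V and D28V) and Tables 43-44 (D5V and D11V). They are also one component of clinical improvement, which is analysed in the ITT population.

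These analyses are only a partial substitute. The visit tables all use ATP populations. Tables 32-34 split visits by setting, and the any-visit row appears only in Tables 43-44, so there is none for Day 28. None counts rescue days, antibiotics obtained without a qualifying visit, or antibiotics for other indications. In clinical improvement, rescue is merged with symptoms and other criteria. Table 73 is untested, and its title covers prior as well as concurrent medications.

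Finally, Tables 30-31 print each arm's mean. The placebo mean is non-study days, and subtracting five from the azithromycin mean gives roughly the same quantity there. This is true, but it is approximate because of overlap, it is confined to subjects who completed five doses, and it is left to the reader.

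**Conclusion.** The concern holds in a limited form. The p-value for secondary objective 1 is essentially determined by the assigned course: with equal rescue the expected difference is about -5 days. With 7- to 10-day courses, placebo rescue would have to exceed azithromycin rescue by roughly 50 to 71 points for the null to be true. The rescue rates, course lengths and 280 per arm are assumptions, but the conclusion does not depend on particular values within the ranges shown. Non-study antibiotic use is not analysed as an endpoint of its own, and the populations chosen can lose subjects who were rescued early.

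The primary analysis is unaffected. A reader might infer that a significant result here could carry the trial's conclusion. SAP 8.1.1 rules that out by resting non-inferiority on the primary analysis alone and calling the others supportive. The DOOR tie-breaker is a separate matter and is not at issue.

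**What to change.** In SAP 8.2.5 and Tables 30-31, keep mean total antibiotic days by arm and the difference with its 95% CI, labelled as net exposure. Drop the p-value, or footnote it as determined by the assigned course. Because Protocol 11.4.2 item 4 specifies the test, dropping it should be recorded in SAP section 13.

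Add two analyses through D11V and through D28V, by randomised arm in the ITT population:

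- the proportion with any non-study systemic antibiotic, with a Miettinen-Nurminen risk difference and 95% CI;
- the mean number of non-study systemic antibiotic days, with the difference and 95% CI.

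State how subjects who leave before the visit are counted. Any illustration of size should give rescue rates and course length as assumptions, with a range.

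The cost is two extra tables, a paragraph of SAP text and one fewer p-value. No new data are needed: Protocol 6.6 already has non-study systemic antibiotics recorded through the last visit.
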